### **6.7.2 Variables Considered**

Standard continuous or categorical variable summaries will be presented for the following variables:

#### **Demography**

- Site number
- Age at screening visit as recorded on the study database (years)
- Sex (Male, Female)
- Ethnicity (Hispanic or Latino, Not Hispanic or Latino)
- Race (American Indian or Alaska Native, Asian, Black or African American, Native Hawaiian or Other Pacific Islander, White, Other). If more than one race is selected then race will be “Other”.
- Height (cm) at Screening visit
- Body weight (kg) at Screening visit
- BMI ( $\text{kg}/\text{m}^2$ ), at Screening visit, calculated as weight (kg) divided by height ( $\text{m}^2$ ) rounded to one decimal place.

#### **Medical History**

Separate tabulations will be produced for previous and ongoing conditions with all conditions coded using MedDRA Version 18.0 (primary system organ class and preferred term).

#### **Smoking & Alcohol History**

- Ever smoked cigarettes (Yes, No). If yes,
  - Number of years used
  - Average number of times used/day
  - Whether currently smoking (Yes, No)

**Alcohol History**

- Was Alcohol ever used? (Yes, No). If yes,
  - Number of years alcohol was used (Yes, No)
  - Currently using (Yes, No)
  - Average number of times consumed/week

**Opioids Abuse**

- Primary Opioid of Abuse (data recorded on the concomitant medication eCRF)
- Duration of substance abuse (years).
- Average number times taken per day.
- IV Use (Yes/No)

**Infectious Disease Panel and Syphilis Tests at Screening**

- Syphilis Antibody (Positive, Negative)
- HBsAg (Reactive, Non-reactive)
- Anti-HBC, Total (Reactive, Non-reactive)
- Hep B Surface Ab (IU/L)
- Anti-HCV (Reactive, Non-reactive)

**Urine Drug Screen at Screening**

- Result, positive for:
  - Amphetamines (Yes, No)
  - Methamphetamines (Yes, No)
  - Cocaine (Yes, No)
  - Barbiturates (Yes, No)
  - Opiates (Yes, No)

- Benzodiazepines (Yes, No)
- Cannabinoids (Yes, No)
- Methadone (Yes, No)
- Buprenorphine (Yes, No)
- Oxycodone (Yes, No)
- Phencyclidine (Yes, No)
- MDMA (Yes, No)

### Prior medications

Verbatim terms (as recorded on the CRFs) of medications that ceased prior to the time of the initial dose of study medication will be mapped to Anatomical Therapeutic Chemical (ATC) Level 2 and Drug Reference Names using the World Health Organization (WHO) dictionary (Version 6.2015 Enhanced). Prior medications will be listed in [Appendix 16.2](#).

### Measurement of Treatment Compliance

Details of compliance will be tabulated overall and for each co-administration category by study day.

Additionally, lofexidine concentration data will be summarized by descriptive statistics for each study day.

### 6.8 Effectiveness Endpoints

#### *Treatment Goal*

Number and proportion of subjects' baseline treatment goal will be presented overall and for each co-administration category.

#### *Status of Pre-defined Withdrawal Treatment Goal as Assessed by the Site Investigator*

Number and proportion of subjects successfully completing their pre-defined withdrawal treatment goal as assessed by the Site Investigator at Day 7 or early termination (last assessment) and Day 14 will be presented overall and for each co-administration category. The number and proportion of subjects who relapsed during the study will be presented overall by study day.

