Effectiveness Endpoints	
 
• Number/proportion of subjects successfully completing their pre-defined withdrawal treatment goal (e.g., planned detoxification/ transition) as assessed by the Principal Investigator.
 
• Distribution of number of days required to complete withdrawal treatment goal by category.
 
• Descriptive evaluation of SOWS-Gossop.
 
• Descriptive evaluation of COWS numerical score and severity score (i.e., mild, moderate, moderately severe, severe).
 
• Concomitant medication analysis.
 
• Evaluation of subject treatment status 30 days after last dose.
 

Duration	23 days (maximum duration per subject, including screening)
Visits	
All subjects will undergo screening up to 9 days before study admission.
 
Days 1-3
 
 
• In-clinic setting: Subjects may be admitted to the clinic on Day -1.
 
 
Days 4-7
 
 
• In-clinic setting OR daily visits for 4 days if outpatient
 
 
Days 8-14
 
 
• Daily outpatient visits for up 7 days
 
 
Day 30
 
 
• Telephone follow-up contact
 

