### 5.2 Categorical

Unordered categorical and ordered categorical (depending on the number of categories) variables will be presented in contingency tables with cell frequencies and percentages for the number of non-missing observations and frequencies for the number of missing observations apart from disposition of subjects, concomitant medications, measurement of treatment compliance and adverse events where percentages will be presented for the population.

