## 6. ANALYSIS PLAN

### 6.1 General

The treatment will be labelled as Lofexidine for presentation of efficacy and safety data. Subject data in [Appendix 16.2](#) listings will be ordered by treatment, site, subject, and study day when applicable.

All tabulations, data listings and figures will be produced using SAS Version 9.3 or higher.

All summaries and analyses documented below will be presented in the final integrated statistical/clinical report and tables that will be based on the E3 guidelines published by ICH.

However, it is noted here that no analysis plan prepared in advance of the data can be absolutely definitive and so the final report may contain additional tables or statistical tests if warranted by the data obtained. The justification for any such additional analyses will be fully documented in the final report.

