## 6.3 Analysis populations

The Enrolled Population includes all subjects screened into the study irrespective of whether they received the study medication.

The Safety Population includes all subjects who received at least one dose of study medication.

With the exception of the disposition table all outputs will use the Safety Population.

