### **6.10 Change to Planned Protocol Analysis**

The following changes have been made to the planned protocol analyses sections:

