**7. TABLES TO BE INCLUDED IN THE CLINICAL STUDY REPORT**

Table            Table Title  
number

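### The visible SAP text has no analysis of the protocol's days-to-goal endpoint and no record of its removal, and its goal-completion summary leaves out the exit status of subjects who leave on Days 8-13

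*SAP*

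**What the plan says.** The protocol synopsis gives six effectiveness endpoints. The first is the number and proportion completing the pre-defined goal. The second is "Distribution of number of days required to complete withdrawal treatment goal by category". Section 17.2 promises descriptive statistics for both. Section 15.1 sets the goal within the 14-day study period. Under Section 15.4.1 the investigator records whether the goal has been reached on Days 1-7 and at each visit on Days 8-14, and Section 15.3.4 requests the same assessment at exit. Section 13.2.1 lets dosing stop on any of Days 8-14.

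SAP 6.8 gives the number and proportion completing the goal "as assessed by the Site Investigator at Day 7 or early termination (last assessment) and Day 14 will be presented overall", with a breakdown by co-administration category. It adds: "The number and proportion of subjects who relapsed during the study will be presented overall by study day". On populations, SAP 6.3 says: "With the exception of the disposition table all outputs will use the Safety Population". For categorical variables, SAP 5.2 gives "cell frequencies and percentages for the number of non-missing observations and frequencies for the number of missing observations". Its exceptions are disposition, concomitant medications, treatment compliance and adverse events. SAP 6.10 opens with "The following changes have been made to the planned protocol analyses sections" and lists three.

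**The concern.** An endpoint that the protocol states twice should be either analysed or openly withdrawn. If the SAP is followed as it reads, days to goal would not be tabulated and nobody reading the study report could tell why.

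The second issue concerns the first-listed endpoint. The goal has a 14-day horizon, and subjects may leave on any day of the second week. A summary at Day 7 and another among those assessed on Day 14 passes over what was recorded for subjects who left between those days. What is at stake is the completeness of the effectiveness description, including the simplest figure a reader would want: the share of treated subjects who were at goal when last assessed.

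**Working it through.** There is no figure in the plan to reproduce. The check sets the texts side by side and then traces each exit group through SAP 6.8.

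**Days to goal**

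1. Five of the six synopsis endpoints have an entry in SAP 6.8: goal completion, SOWS-Gossop, COWS, concomitant medications, and status at the 30-day follow-up. Days to goal has none.
2. It cannot be recovered from the planned output. Proportions at Day 7 and Day 14 do not give a distribution over 14 days.
3. The methods section offers no substitute. Protocol 17.1 plans Kaplan-Meier quartiles for variables subject to censoring. SAP 5.1 covers only variables not subject to censoring, SAP 5.2 covers categorical variables, and Section 5 contains nothing else.
4. The three changes in SAP 6.10 are a methadone-assisted cohort, adverse event summaries by inpatient and outpatient phase, and a count of missing standing vital signs. All are additions, and none concerns this endpoint.
5. Sections 7 and 8, including "TABLES TO BE INCLUDED IN THE CLINICAL STUDY REPORT", show column headings with no titles beneath. The SAP contents list puts Sections 7, 8 and 9 all on page 18, so a long table list there is unlikely. The end of the document is not in the available copy, so one cannot be ruled out.

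**Goal completion**

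| Subject leaves | Day 7 or early termination summary | Day 14 summary | Exit assessment used? |
|---|---|---|---|
| Before Day 7 | Last assessment | Missing | Yes |
| On Day 7 | Day 7 status | Missing | Yes |
| Days 8-13 | Day 7 status | Missing | No |
| Day 14 | Day 7 status | Day 14 status | Yes |

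Let N be the number treated, and assume each has at least one assessment. Write:

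- E for the number at goal at last assessment among those who leave by Day 7;
- D and X for the numbers at goal on Day 7 and at exit among those who leave on Days 8-13;
- F and G for the numbers at goal on Day 7 and on Day 14 among the n14 subjects assessed on Day 14.

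Then:

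- First summary = (E + D + F)/N.
- Second summary = G/n14, because SAP 5.2 uses non-missing observations and goal completion is not among its exceptions.
- At goal at last assessment = (E + X + G)/N.

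X appears in neither planned summary. Using the exit value instead of the Day 7 value would change the first summary by (X - D)/N. In absolute terms that cannot exceed the share of treated subjects who leave on Days 8-13. It is zero if there are none. The documents give no goal, continuation or stopping rates, so no number can be put on it.

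**The case against.** The strongest case against the first part is that unseen text is not missing text. A table title for days to goal may exist, and SAP 6.1 says that "the final report may contain additional tables or statistical tests if warranted by the data obtained". This stands as a limit: a reader might infer that the sponsor deliberately removed the endpoint, and the documents do not show that. But a permission to add tables is not a commitment to this one. A bare title would also leave open which day counts and how subjects who never reach goal are handled.

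On the second part, the natural function of the early-termination phrase is to supply a value for subjects who have no Day 7 assessment. SAP 6.6 points the same way by counting one dose on Day 7 as completing the study, although that is a disposition definition. A reader might infer that SAP 6.8 is evenly ambiguous, or that Day 8-13 exits could land in either summary. That is too strong. Replacing an observed Day 7 value with a later one under a Day 7 label is a strained reading, and it changes which value enters the first summary, not which summary the subject enters.

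SAP 5.2 also requires a count of missing observations, so a reader can rebase the Day 14 count on all treated subjects. This is true, but the rebased figure is G/N, which still omits X.

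Two further inferences should not be drawn. Nothing in the SAP proposes adding the two summaries, so subjects appearing in both is not a fault. And although relapse is tabulated, no text links relapse to a change in goal status. The investigator's question can be read cumulatively, so the point does not rest on reversals.

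**Conclusion.** Both parts hold, with medium confidence. The visible SAP neither analyses days to goal nor records its removal, subject to the headings-only state of Sections 7 and 8. On the natural reading of SAP 6.8, the exit assessments of subjects leaving on Days 8-13 go unused and the share of treated subjects at goal within the 14-day window is not reported.

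The first part affects one whole endpoint of six. The second is of unknown size, bounded by the proportion of treated subjects who leave on Days 8-13, and possibly zero. It assumes that the early-termination wording stands in for a missing Day 7 assessment and that SAP 5.2 governs the Day 14 percentage.

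A reader might infer that the study's main conclusion is at risk. It is not. Protocol Section 7 makes safety the primary objective and treats effectiveness as a further interest, and all these summaries are descriptive. The change should be made, but the study does not fail without it.

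**What to change.** In SAP 6.8:

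1. Tabulate the number and percent of the Safety Population by study day of the first Yes on goal completion (Days 1-14). Split those who never reach goal into subjects who left before Day 14 and subjects followed to Day 14. Alternatively, give Kaplan-Meier quartiles under protocol 17.1 with a stated censoring rule. Say what category means in the protocol's endpoint. If the endpoint was dropped on purpose, record and justify that in SAP 6.10 instead.
2. Add the number and proportion of the Safety Population with goal reached as of the last available assessment (exit or Day 14). Count no recorded Yes as not reached, and label this as a conservative convention.
3. State whether the Day 7 value or the exit value is used in the first summary for subjects who leave on Days 8-13.

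The cost is a few sentences of SAP text and one or two descriptive tables. The daily and exit assessments are already scheduled, so no new data are needed and no study procedure changes.

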#### *Questionnaires*

Summary statistics will be provided overall and for each co-administration category by study day for Days 1-14:

- SOWS-Gossop

- COWS

#### *Concomitant Medications*

For each of Days 1 to 14, each subject's number of concomitant medication taken will be treated as a continuous variable. Descriptive statistics will be provided on the as-observed data on each study day and also overall study days.

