### **13.4 Nicotine Replacement Therapy**

Subjects may be permitted to smoke during their in-clinic participation in study based on individual site policy. If they usually use tobacco products, they will be offered and encouraged to use nicotine replacement therapy (patch, gum, inhaler, or nasal spray) while they are in the in-clinic facility to treat their nicotine withdrawal symptoms. If smoking is permitted by a participating site, smoking breaks outside of the in-clinic facility must be constantly observed and supervised.

The estimated total number of tobacco products used by subjects per day during in-clinic treatment will be recorded in the subject's source document and on the eCRF.

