#### **14.6 Concomitant Therapy**

If the individual withdrawal treatment goal requires a specific concomitant medication (e.g., agonist-assisted total withdrawal, transition to buprenorphine or naltrexone, dose reduction of maintenance therapy), that concomitant medication is allowed. At no time are clonidine, tricyclic antidepressants, and beta-receptor blockers allowed (see Section 12.8).

Other concomitant medications or therapies are permitted throughout the study in either an in-clinic or outpatient setting, as clinically warranted. The following medications were found to be useful in earlier lofexidine efficacy/safety studies and, for consistency, the Principal Investigator/study physician/assigned staff may consider their use in this study as appropriate.

1. Guaifenesin (for cough).
2. Alumina, Magnesia, and Simethicone (for emesis and nausea).
3. Dioctyl sodium sulfosuccinate and psyllium hydrocolloid suspension (for constipation).
4. Bismuth sulfate (Pepto-Bismol®) and loperamide (Imodium®) (for diarrhea).
5. Acetaminophen and nonsteroidal anti-inflammatory drugs (NSAIDs) (for headache, muscle aches, or other discomfort).

6. Zolpidem, trazadone, and other benzodiazepines (for insomnia, depression, anxiety).

The Principal Investigator/study physician/assigned staff should contact the Sponsor's Medical Monitor regarding any questions on concomitant medications.

The site should document in source any symptom that requires administration of any concomitant medication as an AE (see Section [15.5.1](#)).

All medications taken will also be recorded in source and on the subject's eCRF along with dose, dates of administration, and reason for use.

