### **15.6.2 Concomitant Medication Administration**

Concomitant medication administration will be recorded daily. All concomitant medications will be recorded in source and in the subject's Concomitant Medication eCRF along with dose, dates of administration, and reason for use.

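### The daily concomitant-medication count in SAP 6.8 does not isolate drugs needed for withdrawal symptoms, and it lacks the cohort split in protocol 17.2

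*SAP*

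**What the plan says.** The protocol synopsis lists "Concomitant medication analysis" among the effectiveness endpoints, and protocol 17.2 includes concomitant medications among the effectiveness measures to be summarised by cohort. Neither place says what the variable is meant to show.

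SAP 6.8 supplies the only definition: for each of Days 1 to 14, "each subject's number of concomitant medication taken will be treated as a continuous variable". It continues: "Descriptive statistics will be provided on the as-observed data on each study day and also overall study days". For the withdrawal scales in the same section the SAP is more specific: "Summary statistics will be provided overall and for each co-administration category by study day for Days 1-14". The concomitant-medication paragraph has no such split.

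The eCRF feeding the count is broad. Protocol 15.6.2 states: "All concomitant medications will be recorded in source and in the subject's Concomitant Medication eCRF along with dose, dates of administration, and reason for use". The SAP's other use of these data is a table in 6.9 by ATC level 2 and drug name. It sits in the safety section and is tabulated overall.

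**The concern.** A variable reported as effectiveness will be read as a sign of how much help subjects needed beyond lofexidine. Only drugs taken for withdrawal symptoms speak to that. As written, the count adds them to drugs that a subject takes because of the treatment goal, a chronic condition or tobacco use. The daily mean can then differ between kinds of subject, or move over days, for reasons unrelated to symptoms. With no split by cohort or co-administration category, the reader cannot see how far the mix of treatment goals drives the figure.

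**Working it through.** The plan states no figure for this measure, so there is nothing to reproduce. The check is mainly textual, followed by simple arithmetic on assumed counts.

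**What can enter the count**

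- *Goal-required drugs.* Protocol 14.6 treats them as concomitant medication: "If the individual withdrawal treatment goal requires a specific concomitant medication", that drug is allowed. Its examples cover agonist-assisted withdrawal, transition to buprenorphine or naltrexone, and maintenance dose reduction.
- *Background drugs.* Protocol 12.8 foresees subjects who stay on antihypertensives, and 14.6 permits other drugs on clinical grounds, apart from clonidine, tricyclics and beta-blockers.
- *Nicotine replacement.* For tobacco users in the clinic, protocol 13.4 says "they will be offered and encouraged to use nicotine replacement therapy". It does not say where this is recorded, so it counts only if entered as a medication.
- *Opioid of abuse.* SAP 6.7.2 lists "Primary Opioid of Abuse (data recorded on the concomitant medication eCRF") as a baseline characteristic. It reaches the daily count only if recorded as taken on or after Day 1, which is conceivable in dose-reduction subjects.
- *Symptomatic drugs.* Protocol 14.6 lists these by symptom.

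**What is kept out.** SAP 6.7.2 classes drugs stopped before the first dose as prior. No other limit, by reason for use, drug class, start date or treatment goal, appears in the text.

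**How the parts combine.** For one subject on one day, write

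N = S + A + G + B,

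where S is non-opioid drugs for withdrawal symptoms, A is an agonist taken as needed for symptoms, G is a scheduled goal-required opioid or naltrexone, and B is everything else. The change between two days is the sum of the four changes.

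*Level.* SAP 6.7.1 defines two co-administration categories by use of buprenorphine or methadone. On any day such a subject takes that drug, N is at least 1, whether the dose is scheduled or for symptoms. A subject in the remaining category can have N = 0.

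*Change, B constant (assumed counts, A = G = 0).* Let S fall from 3 to 1.

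| B | N before | N after | Absolute change | Relative change |
|---|---|---|---|---|
| 0 (S alone) | 3 | 1 | −2 | −2/3 = −67% |
| 1 | 4 | 2 | −2 | −2/4 = −50% |
| 2 | 5 | 3 | −2 | −2/5 = −40% |
| 3 | 6 | 4 | −2 | −2/6 = −33% |

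Constant background drugs raise the level and dilute a percentage change. They leave the absolute change intact.

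*Change, G or B moving (assumed).* If a scheduled goal drug starts on the day one symptomatic drug stops, the change in N is +1 − 1 = 0. If the goal drug starts and no symptomatic drug stops, it is +1. If a recorded nicotine product stops when the subject leaves the clinic, it is −1 with symptoms unchanged. Discharge to outpatient treatment is possible from Day 4.

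**The split.** Protocol 17.2 asks for effectiveness measures by cohort. SAP 6.8 applies co-administration categories to the treatment goal, SOWS-Gossop and COWS, but states none for this count. SAP 6.10 does not list the omission among its changes to the planned analysis.

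**The case against.** The strongest reply is that nobody claims this variable measures need for symptom relief. The protocol gives it a bare name, and a total daily drug count is a crude but legitimate description. Residual withdrawal is measured directly each day by SOWS-Gossop and COWS. Protocol 14.6 has symptoms that need medication documented as adverse events, and SAP 6.9 tabulates withdrawal-related TEAEs by preferred term, phase and co-administration category. The ATC table separates drug types. SAP 6.1 allows further tables, and the SAP's table list shows no titles in the public text, so other medication outputs cannot be ruled out. All of this stands, and it limits the size of the point. It does not supply a daily count by reason for use.

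Three stronger inferences are tempting and should be resisted.

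- A reader might infer that the count would rank subjects wrongly: someone on buprenorphine-assisted withdrawal with several background drugs could score above someone in abrupt withdrawal who needs three symptomatic drugs. No ranking of subjects is planned, any such pair is assumed, and the buprenorphine subject cannot be scored as zero on symptomatic drugs. Protocol 15.1 describes agonist-assisted withdrawal as an agonist taken when needed for symptom relief.
- For the same reason, a reader might infer that every goal-required opioid should be excluded. That would discard as-needed agonist use, which is itself evidence of residual withdrawal.
- A reader might infer that everything on the eCRF is counted, the opioid of abuse included. Drugs stopped before the first dose are not, and the SAP names the opioid of abuse only as a baseline item.

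**Conclusion.** The point holds in a limited form. The SAP 6.8 count includes symptomatic drugs but does not isolate them, and scheduled goal drugs, background drugs and probably nicotine replacement can raise or shift it without any change in symptoms. Saying that the count fails to measure symptom relief at all would go beyond the documents, which never state its purpose. The missing cohort split is a separate departure from protocol 17.2.

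The severity is minor. The summary is descriptive, in an open-label single-arm safety study, with no test or decision attached, and other outputs cover residual withdrawal. The real size is unknown because the documents give no medication counts; the arithmetic above shows direction only. The conclusion assumes that the count will be programmed as written, from all eCRF entries not stopped before the first dose.

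**What to change.** In SAP 6.8, add as the effectiveness summary the daily number of medications whose recorded reason for use is an opioid-withdrawal symptom, and the percentage of subjects with at least one.

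- Report agonists taken as needed for symptoms (protocol 15.1) on a separate line, neither dropped nor pooled with non-opioid symptomatic drugs.
- Leave out scheduled goal-required opioids and naltrexone, nicotine replacement, opioids of abuse, and drugs started before Day 1 for other indications.
- Present the result by day, over all days, and by co-administration category.
- Keep the all-medication count as a separate descriptive table.

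The eCRF already collects reason for use and dates, so no site procedure changes. The cost is SAP wording, a derived flag and medical coding of reason for use before database lock, preferably without sight of the scale scores. Separating scheduled from as-needed agonist doses depends on how clearly sites recorded the reason; entries that cannot be classified should be shown as such.
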